#### Part B:

A sample size of 84 subjects (14 each in DLBCL, MCL, FL, PTCL, MF and CLL) will be enrolled. The null hypothesis that the true response rate is 0.05 will be tested against a one-sided alternative. A total of 14 patients will be accrued in each cohort. The null hypothesis will be rejected if at least 3 responses are observed in 14 subjects. This design yields a type I error rate of 0.02 and power of 0.9 when the true response rate is 0.4.

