## **15.10 Interim Analysis**

An interim analysis is not applicable to this study. As this is an open-label study, appropriate analyses will be conducted on an ongoing basis.

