## **6.5 Significance Level**

Unless otherwise specified, all statistical analyses will be conducted using a one-sided significance level ( $\alpha$ ) of 0.05 and one-sided hypothesis testing.

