## **9.1 Evaluation of Disease Status**

### **9.1.1 DLBCL, MCL, FL, PTCL**

For cohorts that have at least 5 subjects at the recommended Part B dose of 75 mg BID, the frequency of responders according to the 2014 Lugano Classification for subjects with lymphoma will be evaluated at each dose level and for each lymphoma subgroup in Part B. Differences in response to therapy based on the molecular subtypes of DLBCL will be explored.

Assessments will be made after every two 28-day cycles of therapy, i.e., starting just before Day 1 of cycle 3 and then just before each odd-numbered cycle, for solid tumor patients and after every 3 cycles, i.e., just before Day 1 of cycle 4 and then just before cycles 7, 10, and 13, etc, for lymphoma patients.

In Part B, response to treatment will be analyzed using the binomial test for each of the disease-specific cohorts (DLBCL, MCL, FL, PTCL, MF and CLL). The dichotomous classifications to be assessed in each binomial test are disease responders versus non-responders. Responders will be considered as subjects with 2014 Lugano Classifications given by Complete Response (CR) or Partial Response (PR), and non-responders as subjects with 2014 Lugano Classifications given by No Response (NR) or Stable Disease (SD), or Progressive Disease (PD). For each binomial test, the null hypothesis is that the rate of disease responders is 5% and the one-sided alternative hypothesis is that the rate of disease responders is greater than 5%. The null hypothesis will be rejected if the p-value is less than 0.05 (i.e., using a one-sided significance level of 0.05).

Summaries for best disease response will be provided by treatment cohort for subjects diagnosed with lymphoma using frequencies (counts and percentages). For Part B, the estimated rate of disease responder and the p-value from the binomial test will be provided by disease-specific cohort (DLBCL, MCL, FL, PTCL, MF and CLL).

Response to treatment will be provided in a data listing by subject.

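### The type I error (0.02) and power (0.9) stated for Part B do not follow from the printed rule of at least 3 responses in 14; the exact values are 0.030 and 0.960

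*Protocol*

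**What the plan says.** Protocol 15.1 sets out the Part B test in full. The null rate and direction are given by "The null hypothesis that the true response rate is 0.05 will be tested against a one-sided alternative". The size is given by "A total of 14 patients will be accrued in each cohort", and the decision rule by "The null hypothesis will be rejected if at least 3 responses are observed in 14 subjects". The error rates come next: "This design yields a type I error rate of 0.02 and power of 0.9 when the true response rate is 0.4". The protocol Synopsis (Sample Size Consideration) and SAP section 4 carry the same design and the same figures.

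Neither document describes a first stage, a futility look or an early stopping rule for the Part B cohorts. Protocol 15.10 says: "An interim analysis is not applicable to this study". SAP section 12 says the same.

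SAP 9.1.1 carries out the test as a one-sided binomial test against 5% in each cohort, with the criterion "The null hypothesis will be rejected if the p-value is less than 0.05 (i.e., using a one-sided significance level of 0.05)". SAP 6.5 sets the same general level of 0.05.

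**The concern.** The sentence claims to give the operating characteristics of the rule printed beside it, and every input needed to check it is in the same paragraph. A reader who does the check gets different numbers for both the type I error and the power.

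Preliminary efficacy is part of the primary objective of Part B, and the rule applies to all six disease cohorts. This is the only place where the attained type I error and the power of that rule are given. The 0.05 in SAP 6.5 and 9.1.1 is a nominal level, not an attained one. The type I error is misstated in the favourable direction: the true value is about 1.5 times the printed one (0.0301/0.02). The mismatch also leaves open whether the figures were calculated for a different design from the one now described.

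**Working it through.** **Inputs** (protocol 15.1, repeated in the Synopsis and SAP section 4): n = 14 per cohort; null rate 0.05; one-sided; reject at X ≥ 3; alternative rate 0.40; single stage (protocol 15.10, SAP section 12). Stated results: 0.02 and 0.9.

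**Formula.** P(X ≥ 3) = 1 − P(0) − P(1) − P(2), where P(x) = C(14, x) pˣ (1 − p)¹⁴⁻ˣ.

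**Type I error, p = 0.05**

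- P(0) = 0.95¹⁴ = 0.48767
- P(1) = 14 × 0.05 × 0.95¹³ = 0.35934
- P(2) = 91 × 0.05² × 0.95¹² = 0.12293
- P(X ≥ 3) = 1 − 0.96995 = **0.0301** (stated 0.02)

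**Power, p = 0.40**

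- P(0) = 0.6¹⁴ = 0.00078
- P(1) = 14 × 0.4 × 0.6¹³ = 0.00731
- P(2) = 91 × 0.4² × 0.6¹² = 0.03169
- P(X ≥ 3) = 1 − 0.03979 = **0.9602** (stated 0.9)

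The plan's figures are not reproduced. The type I error rounds to 0.03. The power rounds to 0.96, or to 1.0 at one decimal. With this rule, power of 0.90 is reached at a true rate of about 0.34 (0.890 at 0.33, 0.904 at 0.34).

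**Could another reading of n = 14 give the stated pair?**

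| Reading | Type I error | Power at 0.40 |
|---|---|---|
| Reject at ≥ 2 | 0.153 | 0.992 |
| **Reject at ≥ 3 (as printed)** | **0.030** | **0.960** |
| Reject at ≥ 4 | 0.004 | 0.876 |
| Normal approximation, ≥ 3 | 0.002 | 0.922 |
| Normal with continuity correction, ≥ 3 | 0.014 | 0.955 |
| Poisson approximation, ≥ 3 | 0.034 | 0.918 |

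None does.

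**Which unprinted designs come close?** With the same cut-off of 3 in a single stage, 12 subjects give 0.0196 and 0.917; 11 subjects (0.0152 and 0.881) and 13 subjects (0.0245 and 0.942) also round to the stated pair. So does a two-stage design within 14 that looks after 5 subjects and stops if there are no responses. That stop removes the paths with 0 of 5 followed by at least 3 of 9:

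- Type I error: 0.03005 − 0.95⁵ × P(X ≥ 3 | 9, 0.05) = 0.03005 − 0.77378 × 0.00836 = 0.0236
- Power: 0.96021 − 0.6⁵ × P(X ≥ 3 | 9, 0.40) = 0.96021 − 0.07776 × 0.76821 = 0.9005

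Several designs fit, so the figures do not identify their own origin, and the documents do not say what it was.

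**Is the SAP criterion consistent with the cut-off?** Yes. At n = 14 the one-sided p-value is 0.153 for 2 responses and 0.030 for 3. The criterion p < 0.05 therefore gives the cut-off of 3, with an attained level of 0.030.

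**The case against.** The strongest counter-argument is that nothing turns on the error. The protocol gives the SAP priority, and the SAP decides by p < 0.05, not by the printed 0.02. At 14 subjects no cohort's result would change. The true type I error is under 0.05, the power is better than claimed, and Part B is an uncontrolled search for preliminary activity. All of this stands and limits the weight of the point. It does not make the sentence correct, and SAP section 4 repeats the same figures, so the priority rule does not remove them.

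A second argument is that 0.030 and 0.96 are themselves conditional on 14 analysed subjects. The primary efficacy population is per protocol, protocol 8.1 speaks of up to 14 per cohort, and SAP 2.3.1.1 allows efficacy endpoints for lymphoma cohorts with as few as 5 subjects at the Part B dose. At small sizes p < 0.05 even selects a different cut-off: with 7 subjects, 2 responses suffice (p = 0.044). This is true and worth stating in the corrected text. It does not rescue the printed figures, because the rule beside them is explicitly 3 in 14, and protocol 8.2 counts its planned numbers as evaluable subjects.

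Third, a dropped first stage is conjecture. That is right: no section supports it, and the finding does not depend on it. It is only a reason for the sponsor to check the source of the figures before correcting them.

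**Conclusion.** The stated operating characteristics are wrong for the printed design. The exact type I error is 0.0301 against 0.02, and the exact power at a true rate of 0.40 is 0.9602 against 0.9. This rests on the printed inputs, a single stage, and all 14 subjects in a cohort being analysed; nothing else is assumed.

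The effect is on what the plan reports, not on what it decides. As a measure of size across Part B: SAP 6.4 plans no multiplicity adjustment. If all six null hypotheses were true and the cohorts independent (both assumptions of this review), the chance of at least one false positive would be 1 − (1 − 0.03005)⁶ = 0.167, against the 1 − 0.98⁶ = 0.114 that a reader would infer from the printed figure. The sentence should be fixed, but neither the sample size, the cut-off nor the test needs to change.

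**What to change.** In the protocol Synopsis, protocol 15.1 and SAP section 4, replace the sentence on error rates with wording such as: *With 14 subjects analysed, this single-stage rule has an exact one-sided type I error of 0.030 and a power of 0.96 at a true response rate of 0.40.*

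Before doing so, the sponsor should check how 0.02 and 0.9 were obtained. If a first stage was intended, describe its size and rule, give the exact operating characteristics of the whole design, and reconcile the text with protocol 15.10 and SAP section 12.

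Optionally, add a note in SAP 9.1.1 that at 14 subjects p < 0.05 is the same as at least 3 responses (2 of 14: p = 0.153; 3 of 14: p = 0.030), with an attained level of 0.030.

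The cost is one sentence in three places and, if wanted, one note. No subjects, cut-offs or analyses change. The stated type I error becomes slightly less favourable and the stated power slightly more so.

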### 15.2 Subject Populations

The following populations will be considered in the statistical analysis of the study:

Safety population: The safety population will include all subjects who take at least 1 dose of study medication. Safety analyses will be conducted using the safety population. The safety population will apply to Parts A, B and C.

PK population: The PK population will include all subjects who receive at least 1 dose of ASN002 and have sufficient plasma concentration data to facilitate the calculation of PK parameters as determined by the pharmacokineticist.

Efficacy Population (EP) will include all subjects who have an evaluable screening and post-dose tumor assessment.

The Per Protocol (PP) population will include all EP subjects without major protocol violations. The PP population will be used as the primary analysis population for efficacy.

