### 5.2 Efficacy Population (EP)

The efficacy population (EP) will include all subjects who have an evaluable screening and post-dose tumor assessment. The EP will be used as the supportive analysis population for summaries and analyses of the efficacy endpoints. No EP will be reflected if Part B is not completed for at least one indication.

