### 5.3 Per-Protocol (PP) Population

The PP population includes all EP subjects without major protocol deviations. The PP population will be used as the primary analysis population for efficacy summaries and analyses. No PP will be reflected if Part B is not completed for at least one indication.

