### **7.1.2 Non-Date Values**

Every effort will be made to obtain required data at each scheduled evaluation from all subjects who have been enrolled. There will be no imputation for missing data.

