# **9 EFFICACY ANALYSIS**

The PP population and EP will be used for summaries and analyses of the efficacy variables described below.

All efficacy results for each lymphoma type will be calculated and presented separately. Efficacy results for solid tumor patients will be shown in listings, and parameters will be shown in text and text tables by range only.

If Part B is not completed for at least one indication, efficacy parameters will only be reported as individual patient listings for summary descriptive reporting in the CSR.

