#### **10.1 Adverse Events**

Treatment emergent adverse events (TEAE) will be classified into a standardized terminology using the Medical Dictionary for Regulatory Activities (MedDRA, version 17.0 or higher) system organ classifications and preferred terms. All summaries of the incidence of treatment-emergent adverse events will be provided using the Safety Population by treatment cohort and overall. Although a preferred term or system organ class may be reported more than once for a subject, each subject will only be counted once in the incidence count for that preferred term or system organ class. Summaries of the following types will be provided:

- Summary of treatment-emergent adverse events;
- Summary of treatment-emergent adverse events by MedDRA system organ class and MedDRA preferred term;
- Summary of treatment-emergent adverse events by MedDRA system organ class, MedDRA preferred term, relationship to study drug, and intensity;

- Summary of serious treatment-emergent adverse events leading to discontinuation from the study by MedDRA preferred term, sorted alphabetically by system organ class and preferred term;
- Summary of treatment-emergent adverse events leading to discontinuation from the study by MedDRA preferred term, sorted alphabetically by system organ class and preferred term.

These summaries will present the number and percentage of subjects reporting an adverse event for each classification level. The denominators for calculating the percentages will be based on the number of exposed subjects in the Safety population (i.e., study drug was administered) in the treatment cohort summarized.

Listing of subject dropouts due to AEs prior to post-dose tumor assessment will be generated. All adverse events, serious adverse events and deaths, and adverse events leading to discontinuation from the study will also be provided in data listings by subject.

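### Treated subjects with no evaluable post-dose tumour assessment are left out of every planned efficacy analysis, which inflates ORR and drops early deaths from PFS and TTP

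*Protocol*

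**What the plan says.** Protocol 15.2 names the primary efficacy set: "The PP population will be used as the primary analysis population for efficacy". PP consists of EP subjects without major violations, so it takes over the EP entry condition, which SAP 5.2 gives as: "The efficacy population (EP) will include all subjects who have an evaluable screening and post-dose tumor assessment". EP is the supportive set. SAP 9 names no third set: "The PP population and EP will be used for summaries and analyses of the efficacy variables described below". The all-treated Safety population serves the safety analyses and, by default, the study-population summaries of SAP 8.

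Nothing brings unassessed subjects back in. SAP 9.1.1 sets CR and PR against NR, SD and PD, with no category for subjects who were not assessed or not evaluable. SAP 7.1.2 adds: "There will be no imputation for missing data". The SAP does foresee early leavers, but only as a listing: "Listing of subject dropouts due to AEs prior to post-dose tumor assessment will be generated".

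The rule has a scope condition. SAP 5.2 says "No EP will be reflected if Part B is not completed for at least one indication" and SAP 5.3 says "No PP will be reflected if Part B is not completed for at least one indication". In that case SAP 9 falls back to listings: "If Part B is not completed for at least one indication, efficacy parameters will only be reported as individual patient listings". SAP 9.1 to 9.4 also limit response, TTP and PFS to cohorts with at least 5 subjects at 75 mg BID.

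**The concern.** Entry to EP depends on something that happens after treatment starts: the subject must live and stay in contact long enough to be assessed. In Part B the first scheduled assessment is at week 12 for lymphoma and week 8 for CLL (Protocol Table 2, footnote i). Those who fail to reach it are likely to include some of the worst outcomes.

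This fits poorly with the endpoints. PFS counts any death as an event (Protocol 15.6.4, SAP 9.4). TTP counts radiographic or clinical progression and death due to tumour progression (Protocol 15.6.3, SAP 9.3). A subject who dies in week 5 without an assessment has a PFS event by definition but is not in the set on which PFS is run.

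Part B has no control arm, so a denominator that drops poor outcomes biases the cohort's result directly. Preliminary efficacy is part of the Part B primary objective, and Protocol 6.4.1 intends the data for later development decisions.

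MF is kept out of the figures below. Its endpoints are set at week 24 and the spleen is palpated every 4 weeks, so the ORR, PFS and TTP arithmetic does not carry over.

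**Working it through.** **1. The plan's own figure.** Inputs from Protocol 15.1 and SAP 4: n = 14, null rate 0.05, alternative 0.40, reject at 3 or more responses. The stated type I error is 0.02 and the stated power 0.9.

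P(X ≥ 3 | 14, 0.05) = 1 − (0.4877 + 0.3593 + 0.1229) = 0.0301, and P(X ≥ 3 | 14, 0.40) = 0.960. The stated pair is not reproduced by the rule as written. That is a separate matter. The present point rests on definitions, and 0.0301 serves only as the baseline in step 6.

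**2. Who is counted.**

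| Treated lymphoma or CLL subject | In EP or PP? | All-treated reading |
|---|---|---|
| Evaluable screening and post-dose assessment | EP yes; PP if no major deviation | Counted |
| Leaves early, has the end-of-treatment disease assessment (Protocol 10.4) | As above, if evaluable | Counted |
| Dies with no post-dose assessment | No | Non-responder; PFS event; TTP event if due to tumour progression |
| Lost with no post-dose assessment | No | Non-responder; no observed event |
| Clinical progression judged by the investigator (Protocol 8.6.5), no scan | Not stated whether this counts as evaluable | Non-responder; PFS and TTP event |

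The secure cases are the third and fourth rows.

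**3. ORR.** Let d be the share of treated subjects with no evaluable post-dose assessment. No responder is lost, so reported ORR = all-treated ORR × 1/(1−d). The documents give no d. The 10% early termination rate in Protocol 8.2 is a different quantity, because some early leavers are assessed at end of treatment. Assumed values:

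| d | 1/(1−d) | P(at least 1 of 14 unassessed) = 1 − (1−d)^14 |
|---|---|---|
| 5% | 1.053 | 0.512 |
| 10% | 1.111 | 0.771 |
| 20% | 1.25 | 0.956 |

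**4. One cohort.** With 14 treated, 2 unassessed and 3 responders, the plan reports 3/12 = 25.0%; all-treated it is 3/14 = 21.4%. The reported one-sided p-value would be 0.0196 (n = 12) instead of 0.0301 (n = 14).

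**5. Week-24 PFS.** Assume 4 of the 12 assessed subjects are progression-free and there is no other censoring. The plan reports 4/12 = 33.3%. On all 14:

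- both excluded subjects died early: 4/14 = 28.6%
- one died, one lost event-free and censored at Day 1: 4/13 = 30.8%
- neither had an event: 4/12 = 33.3%, no change

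**6. The binomial decision.** Suppose 14 are treated with no replacement and the true all-treated ORR is 5%. Then M ~ Bin(14, 1−d) subjects are evaluable, each responding with probability 0.05/(1−d). The test rejects when the exact one-sided p-value is below 0.05, with at least 5 subjects. The critical count is 2 for 5 to 7 evaluable subjects and 3 for 8 to 14. The rejection probability is 0.0301 at d = 0, 0.0301 at d = 10% and 0.0307 at d = 20%.

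If cohorts were instead filled to 14 evaluable subjects, P(X ≥ 3 | 14, 0.05/(1−d)) is 0.039 at d = 10% and 0.053 at d = 20%. Protocol 8.2 counts evaluable subjects, which allows that reading. Protocol 8.1 (up to 14 per cohort), 9.3.1 (replacement only for non-compliance or protocol violations) and 15.1 point against it.

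**The case against.** The best defence is that this is an open design choice in an exploratory, uncontrolled study. The population is clearly defined, protocol and SAP agree on it, and the overall sample size is expressed in evaluable subjects. An event definition and an analysis population are separate things, so PFS is not strictly contradicted.

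The number affected may also be small. Eligibility asks for a life expectancy of at least 3 months, about the time of the first lymphoma scan, and Protocol 9.3 calls for end-of-treatment procedures in anyone who discontinues. Exclusions are visible in listings and population counts (Protocol 15.3, SAP 8.1, SAP 10.1), so a reader could rebuild an all-treated ORR. A shift from 21.4% to 25.0% is small beside exact 95% intervals of 4.7% to 50.8% and 5.5% to 57.2%.

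Several of these points stand. The test is almost unaffected. The size of the bias is unknown because d is unknown. A subject lost without an observed event takes a denominator place from ORR but no event from PFS or TTP. The issue does not arise if Part B completes no indication.

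The rest does not remove the problem. An end-of-treatment visit cannot recover a death or a loss, and Protocol 9.3 allows for subjects who refuse it. A listing is not a planned estimate. Wide intervals describe sampling error and do not correct a denominator that errs in one direction. Nor does openness about the definition settle whether the set suits an endpoint that counts every death.

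**Conclusion.** The concern holds and should be fixed. It follows from the definitions alone: PP and EP both require an evaluable post-dose assessment, no other efficacy set is planned, and no rule returns unassessed subjects as non-responders or as events. It applies when Part B is completed for at least one indication, to the lymphoma and CLL cohorts for which response, PFS and TTP are reported.

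The direction for ORR is certain whenever at least one subject is unassessed and at least one responds: it is overstated by the factor 1/(1−d). PFS and TTP are biased upward only to the extent that the excluded subjects had events. The amounts depend on assumed values of d, so confidence is high on the mechanism and limited on its size. The go/no-go rule on 3 responses is essentially unaffected under the replacement rule as written.

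**What to change.** In Protocol 15.2 and SAP 5 and 9:

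- Make the primary Part B efficacy set all subjects in the cohort who took at least one dose.
- Count subjects with no post-dose assessment, or a non-evaluable one, as non-responders, including for the MF week-24 response endpoints. State the same treatment for any subject without an evaluable screening assessment.
- Where PFS and TTP are reported, run them on this set. Early deaths and clinical progressions are events under each endpoint's own definition; event-free unassessed subjects are censored at Day 1.
- Keep EP and PP as supportive.
- State whether the 14 per cohort are treated or evaluable subjects.

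The cost is SAP wording and a short protocol clarification, with no new data or subjects. Reported ORR will fall in proportion to the unassessed share: by 10% relative at d = 10%, or from 25.0% to 21.4% in the 2-of-14 example. One limit remains: follow-up ends about 30 days after the last dose, so later deaths of early leavers may still go unobserved.
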